## 1. INTRODUCTION

### 1.1. BACKGROUND

Sepsis is life-threatening organ dysfunction due to severe infection and affects 250,000 patients annually in the UK (pre-COVID-19), of whom 48,000 die. In addition, virtually all COVID-19 intensive care unit (ICU) deaths had sepsis. It is a leading cause of death and the most expensive condition treated in hospitals. It was recognised as a top research priority by the James Lind Alliance, a partnership of patients and clinicians to prioritise the most pressing unanswered questions facing the NHS.

The cornerstone of sepsis resuscitation is the administration of intravenous fluids and/or vasopressors (drugs that squeeze the blood vessels to increase blood pressure) to maintain blood flow to prevent organ failure. However, there is huge uncertainty around the individual dosing of these drugs in an individual patient, partially due to high sepsis heterogeneity. The current guidelines provide recommendations at a population-level but fail to individualise the decisions. Wrong decisions lead to poorer outcomes and increased ICU-resource use. A tool to personalise these medications could improve patient survival.

We have developed a new method to automatically and continuously review and recommend the correct dose of these medications to doctors, which was created using artificial intelligence (AI) techniques applied to large medical databases. The method we used is called reinforcement learning. In this framework, we model patients with sepsis in the ICU as belonging to a large number of possible disease states, and we analyse what interventions are likely to help them transition to healthier states, and

eventually to survival. We demonstrated in our initial publication that the value of the AI selected strategy was on average reliably higher than human clinicians. In a large validation cohort independent from the training data, mortality was lowest in patients where clinicians' actual doses matched the AI decisions: mortality rates rose, in a dose dependent manner, as the clinicians' actual decisions diverged from the AI decisions. We have estimated that our AI algorithm could reduce mortality by 10% (in relative terms), which represents over 1,000 lives saved annually in the UK and would scale to hundreds of thousands of lives worldwide. Now, we intend to start clinical testing of this AI technology in the UK.

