### Hypotheses:

- We are able to run the system with high availability, reliability and acceptable lag (near real-time) at the bedside.
- The quality of AI suggestions, assessed by off-duty clinicians, is appropriate.
- Patients' outcomes are better when actual doctors' decisions match the suggested AI decisions (which remain hidden from on duty doctors).

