### Secondary objectives:

- In the shadow mode study, human evaluators will assess the AI decisions: off-duty clinicians will evaluate the clinical correctness/appropriateness of AI suggested decisions. The evaluators will classify the AI suggested actions in different categories, such as “likely safe”, “likely inappropriate”, “possible too low”, or “possibly too high”.
- We will document learning points and develop standard operating procedures for deploying the tool in various hospital systems
- Finally, we will estimate patients’ outcomes (organ failure, ICU mortality and hospital mortality) if the AI decisions were followed and compare them to actual outcomes (which were linked with human decisions).

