## 7. STATISTICS AND DATA ANALYSIS

Data and all appropriate documentation will be stored for a minimum of 10 years after the completion of the study, including the follow-up period.

Data of interest	Statistical analyses
-------------------------	-----------------------------

System / usability data	Simple descriptive statistics (e.g. average system lag, number of technical issues per week...)
Anonymised patients' data	Simple descriptive statistics of the patient characteristics. Comparison of the training and prospective cohorts (simple parametric and non-parametric tests comparing demographics, severity of illness, etc).
Evaluators' data (the doctors assessing the AI in the background)	Descriptive statistics from evaluators data: Agreement between initial human evaluator doses (data point #1) and AI decisions (data point #2), and between AI decisions (data point #2) and actual doses given to patients (data point #3). Proportion of AI decisions (data point #2) classified as appropriate / possibly too low / possibly too high Proportion of human decisions (data point #3) classified as appropriate / possibly too low / possibly too high
AI decisions evaluation	Quantitative analyses of AI decisions: estimate patients' outcomes if the AI decisions were followed and compare them to actual outcomes (which were linked with human decisions). We will use 2 methods: 1) compare short-term outcomes between model-concordant treatment and model-non-concordant treatment, with confounder adjustment; 2) off-policy policy evaluation of the AI policy in the prospective ICHT cohort.

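### Method 1 in section 7 compares AI-concordant with non-concordant care, which is a different quantity from the stated target of AI-followed versus actual outcomes

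*Protocol*

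**What the plan says.** The last secondary objective in protocol section 2 is to estimate patients' outcomes ("organ failure, ICU mortality and hospital mortality) if the AI decisions were followed and compare them to actual outcomes"). Section 7, in the row on evaluating AI decisions, repeats the aim: outcomes "if the AI decisions were followed and compare them to actual outcomes". It then names two methods for this one aim:

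- Method 1: "compare short-term outcomes between model-concordant treatment and model-non-concordant treatment, with confounder adjustment".
- Method 2: "off-policy policy evaluation of the AI policy in the prospective ICHT cohort".

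Section 1.2 separately states a third hypothesis, that "outcomes are better when actual doctors' decisions match the suggested AI decisions".

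Section 7 also plans a descriptive analysis of agreement between the AI's doses and the doses actually given. No concordance share is assumed anywhere, and no step turns the method 1 contrast into a comparison with actual outcomes.

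**The concern.** Actual outcomes come from a mixture of decisions: some matched the AI and some did not. Method 1 takes the matching decisions out of the comparator and places them on the AI side. What remains is matched against unmatched care, which is not what the objective asks for.

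If section 7 is followed as written, the method 1 result will be reported as the difference between following the AI and actual care. It would stand beside the off-policy estimate, which does target that difference, as though both measured the same thing. A reader planning the next stage could take the method 1 figure as the gain to expect from adopting the tool. An analysis plan that faithfully added detail to section 7 would inherit the mismatch.

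**Working it through.** The protocol states no effect size, power or concordance figure for this analysis, so there is nothing to reproduce. The check is a derivation.

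**Notation.** C = 1 if the dose given matches the AI; X = confounders; p(X) = P(C = 1 | X); p = the mean of p(X), the concordance share; mu1(X) and mu0(X) = mean outcome under concordant and non-concordant treatment. Assume full confounder control and one decision point.

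**Quantities.**

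- Actual care: E[Y] = E[p(X)mu1(X) + (1-p(X))mu0(X)]
- AI followed: E[mu1(X)]
- Stated target, AI-followed minus actual: E[(1-p(X))(mu1(X)-mu0(X))]
- Method 1, averaged over the cohort: E[mu1(X)-mu0(X)]

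The two differ by the weight 1-p(X) inside the expectation.

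**Case A: effect unrelated to p(X).** The target is (1-p) times the contrast, so the contrast is 1/(1-p) times the target. Because p is not in the protocol, it is varied here as an assumption.

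To give the ratio a scale, take section 1.1, which says sepsis "affects 250,000 patients annually in the UK (pre-COVID-19), of whom 48,000 die": 48,000/250,000 = 19.2%. The same section says "We have estimated that our AI algorithm could reduce mortality by 10% (in relative terms"), so an AI-versus-actual difference of 0.10 × 19.2 = 1.92 percentage points. This is only an illustration: the 19.2% is for all UK sepsis, not this ICU cohort, and method 1 uses short-term outcomes.

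| p | 1/(1-p) | Contrast when the target is 1.92 points |
|---|---|---|
| 0.1 | 1.11 | 2.13 |
| 0.3 | 1.43 | 2.74 |
| 0.5 | 2.0 | 3.84 |
| 0.7 | 3.33 | 6.4 |

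Check at p = 0.5: mu1 = 19.2 - 1.92 = 17.28; mu0 = (19.2 - 0.5 × 17.28)/0.5 = 21.12; contrast = 17.28 - 21.12 = -3.84.

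**Case B: effect varies with p(X).** Take two equal strata with mean p = 0.5, so that 1/(1-p) = 2.0. Effects are in percentage points.

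| Concordance by stratum | Effects | Method 1 contrast | Target | Ratio |
|---|---|---|---|---|
| 0.8 / 0.2 | -6 / -2 | -4.0 | -1.4 | 2.86 |
| 0.8 / 0.2 | -2 / -6 | -4.0 | -2.6 | 1.54 |
| 0.8 / 0.2 | 0 / -6 | -3.0 | -2.4 | 1.25 |
| 0.9 / 0.1 | -6 / +2 | -2.0 | +0.6 | -3.33 |

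First row: target = 0.5 × 0.2 × (-6) + 0.5 × 0.8 × (-2) = -0.6 - 0.8 = -1.4; contrast = 0.5 × (-6) + 0.5 × (-2) = -4.0; ratio 2.86. In all four rows the ratio returns to exactly 2.0 if the contrast is standardised to the non-concordant group. Section 7 does not say to which group it will be standardised.

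**The case against.** Much can be said for the plan as it stands.

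- **Method 1 suits a stated hypothesis.** It tests the third hypothesis of section 1.2 directly. That stands, and is a reason to keep the contrast, but section 7 does not present it as that test.
- **Method 2 addresses the target.** A reader might infer that the objective has been left without a valid method. The protocol does not support this, since off-policy evaluation aims at the value of the AI policy. It is, however, limited to the ICHT cohort, while section 3 includes a UCLH unit.
- **The inflation factor is conditional.** A reader might infer that method 1 overstates the difference by 1/(1-p) in general. Case B shows otherwise, p is unknown, and at p = 0.1 the factor is only 1.11. Non-concordant care also pools doses above and below the AI's, which makes a constant effect a strong assumption.
- **The direction is not secured.** Patients have repeated decisions, and section 7 does not say whether concordance is judged per decision or per course. A contrast for a single decision could be smaller than the effect of following the AI throughout.
- **Estimation detail belongs in an analysis plan.** That is fair for the choice of estimator and interval. The mismatch between aim and comparator is in the protocol's own text.
- **Stakes are limited.** This is a secondary objective of a shadow-mode study whose primary objective concerns how the software performs technically, and no decision rule rests on method 1.

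**Conclusion.** The mismatch is definite: method 1 is listed as a way to compare AI-followed with actual outcomes, but its comparator is non-concordant care only. This needs no assumption beyond some decisions matching the AI and some not.

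The size is not known. The factor 1/(1-p) applies only under the conditions of Case A (one decision point, full confounder control, a difference scale, an effect unrelated to the chance of concordance) and for a p that the protocol does not give. It would be wrong to conclude that the protocol is bound to exaggerate the AI's benefit, or to attach one figure to the exaggeration. What can be said is that the contrast differs from the target by an amount that the plan does not control.

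A narrower gap goes with it. Method 1 covers short-term outcomes, which can serve the organ-failure part of the objective but not ICU or hospital mortality. The only other listed method is confined to ICHT. The change is worth making, and the primary objective is unaffected.

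**What to change.** In section 7:

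1. Label the adjusted concordant versus non-concordant contrast as the test of the third hypothesis in section 1.2.
2. For the section 2 objective, report the confounder-standardised mean short-term outcome with the decision set to AI-concordant, minus the observed mean over the same decisions, with a patient-level bootstrap interval. This estimates E[(1-p(X))(mu1(X)-mu0(X))] directly and needs no constant-effect assumption, though it still needs confounder control.
3. Show beside it the agreement between AI doses and doses given, which is already planned, so that the reader can see the concordance share.
4. State that method 1 covers short-term outcomes only, and that any mortality estimate under the AI from method 2 applies to the ICHT cohort only unless method 2 is extended to UCLH.

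The cost is some wording and one standardisation step on data already collected. Under a constant effect, the reported difference will be smaller than the raw contrast.

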## 3. STUDY DESIGN

This study is a prospective multi-centre observational study that will include four intensive care units from two different NHS Trusts.

The duration of the study will be up to 24 months.

We will include 100 to 300 adult patients with early sepsis in ICU (within 24h of ICU admission). This number is a pragmatic, realistic estimate of how many patients will satisfy the inclusion criteria in the study period (assuming a conservative 60 admissions per month on each unit (reality is closer to 80-100 pre-COVID-19), and 20% sepsis at admission), and will allow us to deliver on the study objectives.

With regards to human assessors, we will include 6 to 15 ICU doctors, mixing senior registrars, ICU fellows and consultants.

The “system” will be a purpose built webapp accessed from a dedicated laptop, connected to an NHS ICT server, with secure login. It will be linked to a duplicate of the Philips ICCA database (Imperial College Healthcare NHS Trust) or the EPIC EHR (UCLH) which contains ICU patient data in near real time (estimated lag of 5 to 15

minutes). The system will be running the AI Clinician algorithm, which processes ICU patient data and outputs a suggested dose of intravenous fluids and vasopressors. Four times a day (every 6 hours), the system analyses newly admitted ICU patients and identify those who fulfil the sepsis-3 criteria. If they do, they will be added to a list of patients for potential inclusion that will be accessible from within the software (and assessed by human evaluator for enrolment).

The system will contain several tabs:

- 1- **Patient screening.** It displays a list of patients screened and highlighted by the system as fulfilling sepsis-3 criteria. The user (human evaluator) has the option to include them into the study, after verification of the inclusion/exclusion criteria (see sections 4.2 and 4.3 for these criteria).
- 2- **Individual patient data.** This screen contains a drop-down list of patients included in the study. After selecting one, the data time series of this individual patient are displayed here, along with the doses of fluids and vasopressors actually given by human “on-duty” doctors and nurses.

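### The concordance test of hypothesis 3 has no reference policy other than actual care, so a favourable result could not be told apart from residual confounding by severity

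*Protocol*

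**What the plan says.** The third hypothesis in section 1.2 expects better patient outcomes when the treating doctors' "decisions match the suggested AI decisions (which remain hidden from on duty doctors". The matching secondary objective in section 2 is to estimate organ failure, ICU mortality and hospital mortality "if the AI decisions were followed and compare them to actual outcomes (which were linked with human decisions".

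The row on evaluation of AI decisions in the section 7 table gives two methods. The first sets short-term outcomes under model-concordant treatment against those under "model-non-concordant treatment, with confounder adjustment". The second is "off-policy policy evaluation of the AI policy in the prospective ICHT cohort". The only comparator named in either place is actual care. No constant, permuted or other negative-control policy appears.

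Section 3 describes a "prospective multi-centre observational study that will include four intensive care units from two different NHS Trusts", so concordance is not randomised. On size it states: "We will include 100 to 300 adult patients with early sepsis in ICU". Section 1.1 reports the same kind of contrast from the earlier validation cohort, where "mortality rates rose, in a dose dependent manner, as the clinicians' actual decisions diverged from the AI decisions".

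**The concern.** Sicker patients are likely to receive more fluid and vasopressor, and bedside clinicians may judge severity better than the recorded fields do. After adjustment for recorded severity, the dose given can then still predict prognosis. A patient whose dose lies close to a moderate recommendation is, on average, less sick than the record suggests. Closeness to that recommendation then looks protective whether or not the recommendation is any good.

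Method 1 as described cannot separate matching the AI from matching a typical dose. A favourable result would be taken as support for one of the study's three hypotheses, and would repeat the pattern in section 1.1, without showing that the AI's individualised advice carries information.

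**Working it through.** The protocol gives no effect size, power or expected odds ratio for this analysis, so there is no stated figure to reproduce. The check asks whether the artefact can arise when dose has no effect at all. Every simulation input below is an assumption.

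**Model A (continuous dose, 200,000 patients)**

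- True severity: S ~ N(0, 1).
- Recorded severity: M = S + N(0, σ²), with σ = 0.5, 0.7 or 1.0. Reliability is 1/(1 + σ²), that is 1/1.25 = 0.80, 1/1.49 = 0.67 and 1/2 = 0.50.
- Dose given: log dose = −0.2 + 0.8 S + N(0, 0.6²).
- Death: logit P = −1.2 + 0.9 S, with no dose term.
- AI dose: f × the fitted geometric-mean dose at M, with f = 0.8 or 1.0.
- Concordant: the 40% of patients with the smallest absolute gap between the dose given and the policy dose.
- Analysis: logistic regression of death on concordance, M and M².

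Adjusted odds ratio of death for concordance (true value 1):

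| σ | f | AI | AI doses permuted | Constant median dose |
|---|---|---|---|---|
| 0.5 | 0.8 | 0.84 | 0.86 | 0.91 |
| 0.5 | 1.0 | 0.94 | 0.89 | 0.91 |
| 0.7 | 0.8 | 0.80 | 0.78 | 0.86 |
| 0.7 | 1.0 | 0.90 | 0.85 | 0.88 |
| 1.0 | 0.8 | 0.72 | 0.71 | 0.83 |
| 1.0 | 1.0 | 0.85 | 0.78 | 0.81 |
| 0 (fully recorded) | – | 0.99–1.01 | 0.99–1.01 | 0.99–1.01 |

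Repeat runs move these values by about 0.02. In all six noisy settings the AI and both uninformative policies look protective. Measuring the gap on the log scale weakens the spurious effect for the two reference policies but does not remove it.

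**Model B (five dose bins, 40% of patients in the zero bin)**

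Mortality is 18.6%, close to 48,000/250,000 = 19.2% from section 1.1. Concordance means the same bin. Dose again has no effect. Adjusted odds ratios by reliability of recorded severity:

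| Policy | 1.0 | 0.8 | 0.6 | 0.4 |
|---|---|---|---|---|
| Constant zero | 0.99 | 0.71 | 0.54 | 0.44 |
| Constant bin 1 | 1.03 | 0.92 | 0.87 | 0.83 |
| Constant bin 2 | 1.01 | 0.97 | 1.01 | 1.02 |
| Given doses shuffled | 0.97 | 0.92 | 0.85 | 0.82 |

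With 300 patients, the chance of a nominally significant benefit (two-sided p < 0.05) across the same reliabilities is 1.5%, 11%, 33% and 54% for constant zero, and 3%, 2.5%, 5% and 6% for shuffled doses.

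**Would requiring the AI to beat the reference policies work?** In model A with σ = 0.7:

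- Useless AI (no effect), f = 0.5: AI 0.65, permuted 0.71, constant 0.85. The useless AI beats both.
- Truly beneficial AI (concordance odds ratio 0.90), f = 1.0: AI 0.82, permuted 0.82, constant 0.83. The useful AI cannot be separated from them.

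The bias differs between policies because permuting breaks the link between the recommendation and recorded severity. A ranking rule can therefore err in both directions.

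**The case against.** The strongest reply is that section 7 is an outline. It defines neither the confounders nor concordance nor the off-policy estimator, and falsification analyses often sit in a statistical analysis plan, which is not at hand. Nothing in section 7 rules them out. This stands as a limit: the point concerns the protocol as written and is not a proven omission from the whole plan. Even so, section 7 does fix the contrast and its comparator, and that contrast is open to this artefact.

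Three stronger readings are tempting, and the documents do not support them.

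- *Hypothesis 3 rests on confounder adjustment alone.* It does not, because method 2 is planned beside method 1. Method 2 is no cure, though: it also depends on measured confounders, covers the ICHT cohort only, and names no reference policy beyond actual care. The evaluators' ratings are separate evidence on the advice, but they do not test outcomes.
- *An artefact would be read as a benefit and carry the tool into its next stage.* The primary objective is technical reliability, outcome estimation is a secondary objective, and no go/no-go rule depends on it. Section 1.1 already foresees the later stage without making it conditional on this result.
- *Any uninformative policy would show the same benefit as the AI.* Model B's constant bin 2 shows none at any reliability, and shuffled doses seldom reach significance at 300 patients. Appendix 2 also lists vital signs, lactate, blood gases, ventilation, renal replacement and fluid balance, so recorded severity may be better than a single noisy score.

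What remains is that the size of the residual confounding is unknown in advance, and the plan as described has no means of showing it.

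**Conclusion.** The concern holds in a limited form. Under method 1 as described, a favourable AI association could not be distinguished from residual confounding by severity, and method 2 does not resolve this. With no treatment effect, recorded-severity noise SD of 0.5 to 1.0 and an AI factor of 0.8 to 1.0, spurious adjusted odds ratios were 0.71 to 0.89 for permuted doses and 0.81 to 0.91 for a constant median dose. They were about 1.0 with severity fully recorded. The direction is plausible for this setting. The size depends on the assumed noise, the policy and the definition of concordance, none of which the protocol gives.

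A reader might infer that the AI should be required to show a stronger association than every reference policy. The calculations do not support that rule, since a useless AI can pass it and a useful one can fail. This is an improvement worth making to a secondary analysis. It does not touch the primary objective.

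**What to change.** In section 7, method 1, and in method 2 where feasible, add that the identical adjusted analysis will be run for two reference policies used only as analysis comparators: the AI doses permuted between patients within time since ICU admission, and one constant cohort-median dose. Report both beside the AI estimate with patient-level bootstrap intervals, so that repeated decisions within a patient are respected.

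State the interpretation in advance, in one direction only. If the reference policies also show apparent benefit, the AI association is not to be read as evidence that the AI's individualised advice improves outcomes. If they do not, that does not certify freedom from bias: constant bin 2 in model B stayed near 1 while constant zero fell to 0.44. Set no pass/fail rule based on the AI being stronger than the references, and judge by estimates and intervals, because significance is a weak guide at 100 to 300 patients.

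The cost is extra analysis work on data already being collected. The conclusion may be less favourable to the AI, a true benefit may go uncredited when the references also look protective, and precision will be limited at the planned size. If a statistical analysis plan already contains such a check, a cross-reference from section 7 is enough.
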